	
whereas safety will be evaluated in the Safety population.
 
• Primary endpoint 
Changes from baseline of TSS scores will be calculated after 4 weeks of treatment. The between-group analysis will be performed by means of a t-test for independent samples or analogous non-parametric test.
 
• Secondary endpoints 
○ Change from baseline of VAS score after 2 and 4 weeks of treatment. The between-group analysis will be performed using a t-test for independent samples or analogous non-parametric test.○ Change from baseline of TSS scores after 2 weeks of treatment. The between-group analysis will be performed by means of a t-test for independent samples or analogous non-parametric test.○ Change from baseline of TSS score for each patient after 2 and 4 weeks of treatment will be classified as $\geq 30\%$ and $< 30\%$, thus defining responder and non-responder patients. Between-group differences will be tested by means of a Chi-square test with 2x2 contingency tables.○ Time to maximum effect on TSS vs placebo will be analysed by means of t-test for independent samples after log-transformation of the data or analogous non-parametric test.○ Between-group differences in the number of patients using rescue treatment will be analyzed by means of a Chi-square test with 2x2 contingency tables.○ Changes from baseline in TNSS, TOSS and TTSS scores will be calculated after 2 and 4 weeks of treatment and between-group differences analyzed using a t-test for independent samples or analogous non-parametric test.○ The number of patients with score for a single symptom ≤ 1 will be calculated and the between-group differences analyzed by means of a Chi-square test with 2xn contingency tables, where n represents the number of observations.○ The intensity of the onset of exacerbations occurring during Period II will be evaluated through the TTS score and compared between the two groups using a t-test for independent samples or analogous non-parametric test.○ The between-group differences in number and duration of exacerbations occurring during Period II will be analyzed by means of a Mann-Whitney U test. 
• Quality of life
--	--

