8.1 INCLUSION CRITERIA

Each patient must meet all of the following inclusion criteria:

- Age 6 to 12 years
- Male or female
- Diagnosis of allergic rhinoconjunctivitis

- Hypersensitivity to dust mites or pollen confirmed with skin-prick test (wheal and redness, ≥ 3 mm more extended than control) performed in the previous 12 months
- Total Symptoms Score (TSS) ≥ 15 and at least 1 for nasal congestion
- Written informed consent of patient and of parent or legal guardian

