9.4 METHOD OF ASSIGNING PATIENTS TO TREATMENT GROUP

For Period I, patients will be randomized with a 1:1 ratio to one of the two treatments (oral Lertal[®] tablets +standard therapy or placebo tablets + standard therapy).

The study product and placebo will be provided in identical boxes and will be identified with a four-digit box number.

The randomization list will be stratified by type of allergy and generated according to permuted blocks codes by an independent statistician through a validated SAS program[®] Software Version 9.4.

The randomization process will be centralized and the assignment to one of the treatments will be carried out through the web-based Electronic Case Report Form (eCRF) system by designated site personnel. When a patient is considered eligible (i.e. he/she fulfils all the inclusion criteria and does not present any exclusion criteria of the Study Protocol), site personnel will access the system in a dedicated section, using a personal account to receive the box number for the incoming patient and will confirm the assignment into the system. Each box number is linked to a treatment code through the randomization list.

A randomized patient is defined as a patient who is registered and is assigned to a box number by the eCRF.

To ensure an adequate number of patients with both types of allergies (pollen and dust mites), the enrollment of patients with dust mite allergies will be blocked should these patients represent 60% of the study population before spring 2018.

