10 ASSESSMENTS

10.1 EFFICACY ASSESSMENTS

10.1.1 Total Symptom Score

The primary variable of the study is the Total Symptoms score (TSS), a patient-reported evaluation of nine symptoms:

- Nasal symptoms (TNSS): itching, sneezing, rhinorrhea, nasal congestion
- Ocular symptoms (TOSS): itching, hyperemia of conjunctiva, tearing
- Throat symptoms (TTSS): itching, coughing

With the help of their parents, patients will score symptoms on a 4-point scale: 0 = absent or irrelevant, 1 = mild, 2 = moderate, 3 = severe.

TNSS is the sum of the scores of nasal symptoms, TOSS the sum of the scores of ocular symptoms and TTSS the sum of throat symptoms.

TSS is calculated as the sum of TNSS, TOSS and TTSS.

At baseline (Visit 2), Visit 3 and Visit 4, and with the help of a parent, patients are asked to assign a score to the symptoms experienced in the last 12 hours and over the previous two weeks.

The overall TSS score is derived as the mean of the two TSS scores related to the symptoms experienced in the last 12 hours and over the previous two weeks.

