13.1 DETERMINATION OF SAMPLE SIZE

160 patients are to be enrolled in this study.

Confidential

A sample of 72 patients for each group will have an 80% power to detect an effect size on the primary variable ($\delta = |\mu_1 - \mu_2| / \sigma$) of 0.47 (medium effect size) (12), using an independent samples t-test with a two-tailed significance level of 5%.

A sample size of 80 patients per group will account for an expected dropout rate of 12% (13), using Freedman's formula (*Control Clin Trials*, 1990): $n' = 100 * n / 100 - x$, where x is the expected dropout rate.

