13.2 STATISTICAL METHODS

13.2.1 Analysis populations

Patients without a valid or adequately obtained Informed Consent Form (ICF) will be excluded from any analysis population.

The following analysis populations have been defined for these statistical analyses:

- Safety: All randomized patients who took at least one dose of study product.
- Intention to treat (ITT): All randomized patients who took at least one dose of study product and have at least baseline and one post-baseline assessment of the primary efficacy variable. Patients who interrupt treatment will be considered as “failures” for qualitative variables and their missing quantitative data will be substituted according to the LOCF method (Last Observation Carried Forward).
- Per protocol (PP): All randomized patients who completed Period I and did not have significant protocol violations that regard inclusion/exclusion criteria or can condition the efficacy evaluation.

The efficacy analysis will be performed on the ITT population and also on the PP population as a supportive analysis for the primary endpoint and reported overall and by planned treatment group. Safety will be evaluated in the Safety population and reported overall and by actual treatment group.

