13.2.2 Statistical Analysis

All data collected in the study will be listed and summarized as appropriate as described below. Continuous data will be summarized by means of common descriptive statistics: mean, standard deviation (SD), median, first and third quartiles, minimum and maximum. Categorical data will be presented by absolute and relative frequencies (n and %) or contingency tables.

For the safety analysis, patients will be included in based on available assessments; no missing data handling approach will be applied. For efficacy analyses, patients who interrupt treatment will be considered as “failures” for qualitative variables and their missing quantitative data will be substituted according to the LOCF method (Last Observation Carried Forward). Unless stated otherwise, two-sided p-values <0.05 will be considered statistically significant.

All statistical tables, listings, figures and analyses will be generated using SAS® release 9.4 or later (SAS Institute Inc., Cary NC, USA).

No interim analyses are planned.

Further details about data analysis will be provided in the Statistical Analysis Plan document.

All data about patient demographics and baseline characteristics will be summarized on the ITT population by treatment group by means of summary descriptive statistics.

The number and percentages of subjects meeting all eligibility criteria at screening will be provided. The analysis populations will be described and the reasons for excluding a patient from any particular population will be provided with the number of protocol deviators per each criterion.

A complete description of patients’ disposition will be provided specifying the number of randomized patients, the number of patients at each visit, the number of completed and discontinued patients and the reason for the discontinuation.

Medical history data will be presented by Medical Dictionary for Regulatory Activities MedDRA dictionary system organ class (SOC) and preferred term (PT).

Concomitant medications and significant non-drug therapies will be presented by WHO Drug Dictionary ATC class and preferred term.

- **Primary endpoint**

Changes from baseline of TSS scores will be calculated after 4 weeks of treatment. The between-group analysis will be performed by means of a t-test for independent samples or analogous non-parametric test.

- **Secondary endpoints**

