- Change from baseline of VAS score after 2 and 4 weeks of treatment. The between-group analysis will be performed by means of a t-test for independent samples or analogous non-parametric test.

- Changes from baseline of TSS scores after 2 weeks of treatment. The between-group analysis will be performed by means of a t-test for independent samples or analogous non-parametric test.
 - Changes from baseline of TSS score for each patient after 2 and 4 weeks of treatment will be classified as $\geq 30\%$ and $< 30\%$, thus defining responder and non-responder patients. Between-group differences will be tested by means of a Chi-square test with 2x2 contingency tables.
 - Time to maximum effect on TSS vs placebo will be analysed by means of t-test for independent samples after log-transformation of the data or analogous non-parametric test.
 - Between-group differences in the number of patients using rescue treatment will be analyzed by means of a Chi-square test with 2x2 contingency tables.
 - Changes from baseline in TNSS, TOSS and TTSS scores will be calculated after 2 and 4 weeks of treatment and between-group differences analyzed by means of a t-test for independent samples or analogous non-parametric test.
 - The number of patients with score for a single symptom ≤ 1 will be calculated and the between-group differences analyzed by means of a Chi-square test with 2xn contingency tables, where n represents the number of observations.
 - The intensity of the onset of exacerbations occurring during Period II will be evaluated through the TTS score and compared between the two groups using a t-test for independent samples or analogous non-parametric test.
 - The between-group differences in the number and duration of exacerbations occurring during Period II will be analyzed by means of a Mann-Whitney U test.
- **Quality of life**

Changes from baseline of the PRQLQ total score will be calculated at the end of Period I (Week 4) and end of Period II (Week 8 or Week16). An analysis of variance for repeated measures will be adopted, isolating the variability due to type of allergy, treatment group, time of observation and their interaction.

- **Safety**

All safety analyses will be performed on the Safety set. No missing data handling approach will be applied.

Results of physical examinations at each assessment will be presented.

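### The primary t-test on Week-4 TSS change uses neither baseline TSS nor the allergy-type stratum, so it may leave precision unused; the test itself is valid.

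*Combined protocol and SAP*

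**What the plan says.** The synopsis and section 13.2.2 describe the primary analysis in the same way. The outcome is the Week-4 change: "Changes from baseline of TSS scores will be calculated after 4 weeks of treatment". The test follows: "The between-group analysis will be performed by means of a t-test for independent samples or analogous non-parametric test". No covariate or stratum term is named. The rank test is not named, and nothing says how the choice between the two would be made.

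Both candidate covariates will be in hand.
- **Baseline TSS** (section 10.1.1): "At baseline (Visit 2), Visit 3 and Visit 4, and with the help of a parent, patients are asked to assign a score".
- **Allergy type** (section 9.4): "The randomization list will be stratified by type of allergy and generated according to permuted blocks codes".

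The plan does model allergy type for quality of life. The PRQLQ analysis of variance in section 13.2.2 is described as "isolating the variability due to type of allergy, treatment group, time of observation and their interaction".

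On missing data, section 13.2.1 says of patients who interrupt treatment that "their missing quantitative data will be substituted according to the LOCF method". The per-protocol set is the one named supportive analysis of the primary endpoint. Section 11.2.3 says that patients who stop treatment permanently remain in follow-up under the protocol's procedures until their scheduled completion. Section 13.2.2 leaves further analysis detail to a separate SAP document, which was not available for this review.

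**The concern.** A change score does use baseline, but it fixes the baseline slope at 1. ANCOVA estimates that slope and is more precise in large samples unless the true slope is 1. If pollen-allergic and mite-allergic children change by different amounts, that variation stays in the error term of an unadjusted test, although the design has already balanced it between arms. At stake is the precision of the trial's main result, from data that will be collected anyway.

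The unspecified rank alternative adds a smaller problem: the primary test is not fully fixed before the data are seen.

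On missing data, the protocol text describes no analysis of the primary endpoint that varies LOCF directly. The per-protocol analysis removes non-completers and protocol violators together. The Week-2 change and the responder analysis bear on LOCF only indirectly.

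**Working it through.** **1. The plan's own power (section 13.1).** Inputs: 72 per arm, standardised difference 0.47, two-sided 5% t-test. Non-centrality = 0.47 × √(72/2) = 2.82 on 142 df. Power = 79.98%, so the stated 80% reproduces.

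**2. Adjusting for baseline.** Let ρ be the correlation of baseline with Week-4 TSS, and r the baseline SD divided by the Week-4 SD. Neither is in the documents; both are assumed.

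Variance ratio, ANCOVA to change score: VR = (1 − ρ²) / (1 + r² − 2ρr). Power uses non-centrality 2.82/√VR on 144 − 4 = 140 df.

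Example, ρ = 0.3 and r = 0.8: VR = 0.91/1.16 = 0.784, non-centrality 3.18, power 88.5%.

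| r | ρ = 0.3 | ρ = 0.5 | ρ = 0.7 |
|---|---|---|---|
| 12/27 = 0.44 | 80.9% | 80.1% | 84.5% |
| 0.6 | 83.5% | 80.5% | 80.7% |
| 0.8 | 88.5% | 84.2% | 80.7% |

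Over a fine grid of r from 0.44 to 0.80 and ρ from 0.3 to 0.7, power runs from 80.0% to 88.5%. When ρ = r the slope is exactly 1, VR = 1, and nothing is gained.

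The low end of r reflects the entry rule, "Total Symptoms Score (TSS) ≥ 15 and at least 1 for nasal congestion". Nine symptoms scored 0 to 3 give a maximum of 27, so baseline can span 12 points and Week 4 can span 27. That is a ratio of ranges, used only as a rough guide to the ratio of SDs.

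As a cross-check, the entry cut was simulated on assumed bounded scores. With equal untruncated SDs of 5, power was 81.8% to 87.5%. Over all 27 settings tried it was 80.2% to 91.5%, with r reaching 0.95 and ρ between 0.16 and 0.57. The grid is therefore illustrative and not a bound.

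On such bounded scores, with 72 per arm and 20,000 trials per setting, type I error was 5.0% to 5.2% for ANCOVA and 4.5% to 5.1% for the t-test.

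**3. Adjusting for the stratum.** Suppose allergy type explains a share R² of the variance of change (assumed). The unadjusted test then has an actual level of about 2[1 − Φ(1.96/√(1 − R²))]. For R² of 2%, 5% and 10% this gives 4.8%, 4.4% and 3.9%.

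Simulation (40,000 trials, an assumed 43/29 mite/pollen split per arm) gave:

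| R² | Type I error, unadjusted | Power, unadjusted | Power, adjusted |
|---|---|---|---|
| 2% | 4.9% | 80.1% | 80.7% |
| 5% | 4.3% | 80.8% | 82.2% |
| 10% | 3.9% | 81.2% | 83.9% |

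The split takes the 60% in section 9.4 as a working mix. There it is a trigger for closing mite enrolment, not a forecast.

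**4. LOCF.** The ITT set needs a post-baseline TSS, so a missing Week 4 is normally filled from Week 2. Let m be the share carried forward, equal in both arms, and f the Week-2 effect as a fraction of the Week-4 effect (assumed 0.5 to 0.75). With the SD held fixed, expected effect = 0.47 × [(1 − m) + m f].

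Section 13.1 supplies the rate: "A sample size of 80 patients per group will account for an expected dropout rate of 12" per cent. If every dropout had a Week-2 value and no Week-4 value, m = 0.12:
- f = 0.5: 0.47 × 0.94 = 0.442, a 6% shrinkage.
- f = 0.75: 0.47 × 0.97 = 0.456, a 3% shrinkage.

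If half of those dropouts left before Week 2, they would fall outside the ITT set. Then m = 0.06/0.94 = 0.064, and the effect is 0.455 to 0.463, a shrinkage of 1.6% to 3.2%.

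**The case against.** The strongest reply is that this is a preference and not an error. The sample size was computed for a t-test and a t-test is used. The change score already draws on baseline. Leaving out the stratum makes a false positive less likely, and every figure for the gain rests on assumed inputs. All of that is true, and it limits the claim to precision. It does not remove the point, because the covariates are already collected, adjustment costs two degrees of freedom, and over the range examined it loses essentially nothing.

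A second reply is that the separate SAP may settle these matters. That is a fair answer on LOCF. It is weaker on the primary test, because the protocol sentence already names that test without covariates.

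A reader might draw stronger conclusions that the documents do not support:
- **That the primary test is invalid or the trial underpowered as designed.** Randomisation makes the t-test unbiased, and its stated power reproduces.
- **That the open choice of test will inflate false positives.** Reporting the smaller of the t-test and Mann-Whitney p-values gave 6.1% in 20,000 simulated null trials with normal data. Nothing in the plan says that this would be done.
- **That children who stop treatment yield no Week-4 TSS.** Section 11.2.3 also mentions last-visit procedures, and the assessment chart has no TSS at Visits 5 and 6. But the same section first plans continued follow-up under protocol procedures, which include TSS at Visit 4. LOCF replaces only missing values.

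**Conclusion.** The point holds as one of precision. As the protocol is written, the primary analysis uses neither baseline TSS as a covariate nor the randomisation stratum, and it leaves the rank alternative open. At 72 per arm and a standardised difference of 0.47, baseline adjustment would move power from 79.98% to somewhere between 80.0% and 88.5% for ρ of 0.3 to 0.7 and r of 0.44 to 0.8. Those inputs are assumptions, and the gain could be nil. A prognostic stratum would make the unadjusted test slightly conservative. The change should be made because it is nearly free, not because the planned answer would be wrong.

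The LOCF matter is secondary and optional. At 12% dropout, equal by arm, with 50% to 75% of the effect present by Week 2, the estimate shrinks by at most about 3% to 6%. It shrinks less if some children leave before Week 2 or are still assessed at Week 4. Unequal dropout could move the estimate in either direction. No type I error or power loss from LOCF is claimed. Nor can it be said that no check is planned, only that the protocol text describes no direct one.

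**What to change.** In section 13.2.2 and the synopsis, replace the primary-endpoint test sentence with a pre-specified ANCOVA of Week-4 TSS change on treatment, baseline TSS and allergy type. State that it is used whatever the distribution looks like, with no data-dependent switch of test. Keep the unadjusted t-test as a sensitivity analysis. If a rank test is wanted, name it in advance as supportive, for example van Elteren stratified by allergy type.

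Optionally, add one sensitivity analysis to LOCF. Either of these would do:
- the Week-4 contrast from a mixed model on Weeks 2 and 4 without LOCF;
- delta-adjusted multiple imputation, worsening missing Week-4 values in the Lertal arm in 1-point TSS steps until the conclusion changes.

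If the separate SAP already contains such an analysis, a cross-reference is enough.

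The cost is a wording change and a few lines of SAS. ANCOVA uses 2 of the 142 degrees of freedom. No patients, visits or assessments are added.

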6.2 SECONDARY

The secondary objective is to evaluate efficacy, safety and quality of life in pediatric patients with allergic rhinoconjunctivitis treated with Lertal[®]. The secondary endpoints are the following:

- Overall symptom control assessed by means of a VAS after 2 and 4 weeks of treatment.
- Change from baseline of the Total Symptom Score (TSS) after 2 weeks of treatment.
- Number of responders (at least 30% reduction of TSS) after 2 and 4 weeks of treatment.
- Time to maximum effect on TSS vs placebo.
- Use of “rescue treatment.”
- Change from baseline of Total Nasal Symptom Score (TNSS) after 2 and 4 weeks of treatment.
- Change from baseline of Total Ocular Symptom Score (TOSS) after 2 and 4 weeks of treatment.
- Change from baseline of Total Throat Symptom Score (TTSS) after 2 and 4 weeks of treatment.

- Issues interfering with quality of life at Baseline (Week 0), after Period I (Week 4) and after Period II (Week 8 o Week 16).
- Number of patients symptom-free or with mild symptoms during Period I.
- Number, intensity and duration of exacerbations during Period II. Exacerbations are defined as the need of an antihistamine medication of any kind, at any dose and of any duration.

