7 STUDY DESIGN

7.1 DESCRIPTION OF THE PROTOCOL

❖ Run-in

The 2-week run-in period consists of two visits: Visit 1 at Week -2 and Visit 2 at Week 0. Visit 1 and Visit 2 may be performed on the same day. During these visits, after having obtained signed informed consent from the patient, the Investigator will gather demographic and medical history data, perform a physical examination of the patients and evaluate their eligibility for the study according to inclusion/exclusion criteria indicated in [Section 8](#). Eligible patients will then be randomized in a 1:1 ratio into two treatment groups and will be dispensed one of the study treatments:

- Lertal® double-layer tablets (1 tab/day for 4 weeks) plus standard therapy (antihistamine).

or

- Lertal® placebo tablets (1 tab/day for 4 weeks) plus standard therapy (antihistamine).

The randomization list will be stratified by type of allergy (pollen or dust mites).

Baseline assessments of patient reported outcomes (PRO) will be collected at Visit 2 (Week 0). The patient will also be given a diary on which to record the use of rescue medication/concomitant medication and the occurrence of adverse events. The diary will also be used to record the occurrence/duration of exacerbations during Period II (need of an antihistamine medication of any kind, at any dose and of any duration).

❖ Period I

Visit 3 (Week 2) and Visit 4 (Week 4) constitute the 4-week double-blinded treatment period (Period I). During these visits, patients will be asked to complete their questionnaires and to return their diaries so information concerning safety (adverse events) and the use of rescue/concomitant medications can be collected. Patients need to return all unused product at both visits to check compliance with treatment. Once all data entry related to Period I has been completed (the Investigator has to certify that the data entered are complete and accurate), the eCRF will make the unblinding procedure available to the investigator so he or she can find out what treatment was

taken by the patient during the double-blinded period. All assessments scheduled for Visit 4 shall be performed prior to unblinding.

A patient that concludes treatment Period I and still presents symptoms that do not permit interruption of standard therapy is considered a non-responder and will not take part in Period II of the study. The patient will be discontinued from the study.

❖ Period II

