10.1.6 Patient diary

Children will be given a diary and asked, together with a parent, to write down any rescue medication/concomitant medications taken, as well as the occurrence of any adverse events. During Period II, the number and duration of any exacerbations (need of an antihistamine medication of any kind, at any dose and of any duration) should be indicated in the diary.

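### The secondary endpoint of time to maximum effect on TSS cannot be measured when TSS is scored after baseline only at Weeks 2 and 4

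*Combined protocol and SAP*

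**What the plan says.** Section 6.2 and the synopsis list "Time to maximum effect on TSS vs placebo" among the secondary endpoints. Section 13.2.2 and the synopsis give the analysis: "Time to maximum effect on TSS vs placebo will be analysed by means of t-test for independent samples after log-transformation of the data", with an analogous non-parametric test as the alternative.

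The measurement schedule is in three places that agree:

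- Section 10.1.1: "At baseline (Visit 2), Visit 3 and Visit 4, and with the help of a parent, patients are asked to assign a score".
- Section 7.1: "Visit 3 (Week 2) and Visit 4 (Week 4) constitute the 4-week double-blinded" treatment period.
- The assessment chart in Section 2 marks TSS at V2, V3 and V4 only.

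Section 10.1.1 also says how each visit's score is formed: "The overall TSS score is derived as the mean of the two TSS scores related to the symptoms experienced in the last 12 hours". The second of these two scores has a recall window of two weeks.

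The diary (Section 10.1.6) is for other data: "Children will be given a diary and asked, together with a parent, to write down any rescue medication/concomitant medications taken", together with adverse events and, in Period II, exacerbations. It carries no symptom scores.

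For patients who interrupt treatment, Section 13.2.2 says "their missing quantitative data will be substituted according to the LOCF method (Last Observation Carried Forward"). It defers further analysis detail to a Statistical Analysis Plan document. Nowhere do the documents define maximum effect, say how ties are resolved, or say what time is given to a child who never improves.

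**The concern.** A time-to-effect variable needs enough observations to locate the effect in time. Here there are two after baseline, so the variable hardly measures time. What remains is whether a child scored better at the second visit than at the first.

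That is a poor stand-in for speed. A child who is still improving at Week 4 is recorded as taking 4 weeks. A child who levels off or worsens after Week 2 is recorded as taking 2. An arm whose benefit keeps growing can therefore look slower than one that stalls. The introduction and synopsis suggest that nutraceuticals may hasten recovery, so a significant result in either direction is likely to be read as evidence on speed of onset, which it would not be.

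**Working it through.** **Plan's own figure.** The plan gives none for this endpoint. Its only sizing statement is for the primary variable: "A sample of 72 patients for each group will have an 80% power to detect an effect size on the primary variable" of 0.47 (two-sided 5%). This reproduces: t-test power at 72 per group and effect size 0.47 is 79.98%. I use 72 per arm below.

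**Step 1. Possible values, per-child reading.** Take the time as the visit with the larger TSS reduction. The scoring visits after baseline are Weeks 2 and 4, so the time is 2 or 4. The 12-hour and two-week recall windows are averaged within a visit. They add no time point, and the longer window blurs timing further. Using actual visit dates would add spread, but that spread would reflect appointment timing.

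**Step 2. What the test compares.** With p the share of children better at Week 4 than at Week 2, mean time = 2(1 − p) + 4p = 2 + 2p. The log is a linear relabelling of a two-valued variable and cannot change the t statistic. Example with 36/72 against 50/72 at Week 4:

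| Version | Result |
|---|---|
| t-test, raw weeks | \|t\| = 2.410, p = 0.0172 |
| t-test, log weeks | \|t\| = 2.410, p = 0.0172 |
| t-test, 0/1 indicator | \|t\| = 2.410, p = 0.0172 |
| Chi-square | p = 0.0174 |
| Mann-Whitney | p = 0.0179 |

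All are comparisons of p between arms. A child who never improves has no time, or time 0, whose log is undefined.

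**Step 3. The other reading.** If the endpoint means the time at which the difference from placebo is largest, the trial yields one number. There are no patient-level values, so neither a t-test nor its non-parametric analogue can be run.

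**Step 4. Direction under the per-child reading.** The documents give no SD, correlation or trajectory for TSS change. Assumed: the same SD at both visits, 4 to 5; Week 2–Week 4 correlation r, 0.5 to 0.7; normal changes. Then

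p = Φ[(mean Week 4 reduction − mean Week 2 reduction) / (SD × √(2(1 − r)))].

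Placebo reduction 6 then 7 (gain 1); Lertal 7 then 9 (gain 2), so Lertal is better at both visits:

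| SD, r | Denominator | p placebo | p Lertal | Mean weeks, placebo | Mean weeks, Lertal |
|---|---|---|---|---|---|
| 4, 0.7 | 3.10 | Φ(1/3.10) = 0.63 | Φ(2/3.10) = 0.74 | 3.25 | 3.48 |
| 4.5, 0.6 | 4.02 | Φ(1/4.02) = 0.60 | Φ(2/4.02) = 0.69 | 3.20 | 3.38 |
| 5, 0.5 | 5.00 | Φ(1/5) = 0.58 | Φ(2/5) = 0.66 | 3.16 | 3.31 |

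Lertal looks slower by 0.15 to 0.23 weeks, about 1 to 1.6 days. By normal approximation with 72 per arm, the test would call it significantly slower in about 15% to 32% of trials.

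**Step 5. Other trajectories, same SD and r.**

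- Constant benefit (Lertal 8 then 9, placebo 6 then 7): the gain is 1 in both arms, so p is identical and the endpoint shows no difference.
- Early benefit (Lertal 8 then 9, placebo 5 then 7): p is 0.58 to 0.63 on Lertal and 0.66 to 0.74 on placebo, so Lertal looks faster and the direction is right.

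**Step 6. Drop-outs.** A Week 2 score carried forward to Week 4 makes a tie. If ties go to the first maximum, an assumption, that child counts as 2 weeks. Suppose 70% of completers are better at Week 4, also an assumption. With no drop-out, mean time is 2 + 2(0.70) = 3.40 weeks. With 12% drop-out after Week 2, it is 2 + 2(0.70 × 0.88) = 3.23 weeks.

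**The case against.** The strongest reply is that much of this depends on a definition the plan has not given. A separate SAP could define maximum effect, ties and non-improvers, and could explain the reference to placebo. That is right, and for that reason a reader should not infer that the plan's definition itself makes the better arm look slower: there is no such definition. The reversal belongs to one natural reading and to assumed trajectories in which Lertal gains more than placebo after Week 2. With an early benefit the direction is correct, and even in the adverse example most trials would give a non-significant result.

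Three further points stand. Speed of effect is not a stated objective: Section 6 names effect on TSS, then efficacy, safety and quality of life, and faster recovery appears only as background. A reader might also infer that LOCF makes drop-outs count as fast. That needs a tie rule the documents lack, and Section 11.2.3 asks that patients who stop be followed and, if possible, assessed. Nor is the test invalid on a two-valued variable: t, chi-square and Mann-Whitney agree closely, so the problem is what the result means.

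None of this meets the central point. A SAP can supply definitions but not TSS scores between visits that the protocol does not collect.

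**Conclusion.** The point holds in this form: the endpoint is undefined and too coarsely measured to describe time to maximum effect. The two-value result needs only the visit schedule, the diary content and the per-child reading. Under the alternative group-level reading, the planned test has no data to work on.

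The size of any distortion is conditional. Under the late-gain assumptions the better arm has a mean time of about 3.3 to 3.5 weeks against 3.2 to 3.3. A constant benefit is invisible, and an early benefit shows correctly. Reversal is therefore possible, not inevitable. The consequence is confined to one secondary endpoint; the primary analysis and the sample size are untouched.

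**What to change.** Delete this endpoint and its test from the synopsis, Section 6.2 and Section 13.2.2. Address early effect with comparisons the plan already contains: the between-arm difference in TSS change and the 30% responder comparison at Week 2, each shown beside its Week 4 counterpart.

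The cost is one uninformative secondary endpoint and a few lines of wording. No new data are needed. Collecting daily symptom scores in the diary would be the way to a genuine time-to-effect measure, but it is not needed for this correction. It adds burden for families, and a daily 12-hour score is not like for like with the visit TSS, which averages two recall windows.
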